### 1.3.2 **Efficacy**

Study ABE4869g did not meet its co-primary efficacy objectives. In the higher dose cohort, a 16.8% treatment effect in the Alzheimer's Disease Assessment Scale-Cognition, 12 questions (ADAS-Cog-12) change score was seen in the mild to moderate AD population (defined as an MMSE score, 18–26) at Week 73 relative to placebo (1.78 point difference; 95% CI, -0.89, 4.44;  $p=0.190$ ) (Cummings et al. 2014; Mackey et al. 2016). The observed treatment effect increased to 23.8% in a prespecified analysis in the mAD population (MMSE score, 20–26; 2.24 point difference; 95% CI, -0.66, 5.15;  $p=0.128$ ) and to 35.4% in a subsequent analysis in patients with an MMSE of 22–26 (3.44 point difference; 95% CI, 0.24, 6.64).

No treatment effect was observed in the Clinical Dementia Rating-Sum of Boxes (CDR-SB) in either the mild to moderate AD population (3.1%; 0.08 point difference; 95% CI, -0.77, 0.92;  $p=0.853$ ) or mild AD population (-1.0%; -0.02 point difference; 95% CI, -1.0, 0.96;  $p=0.964$ ). In an exploratory analysis of a subset of patients with milder AD (MMSE, 22–26), the treatment effects for CDR-SB change from baseline to Week 73 scores relative to placebo increased to 19.6% (1.8 point difference favoring crenezumab; 95% CI, -0.65, 1.52).

In the lower dose (300 mg q2w) SC crenezumab cohort, no treatment effect was observed on the ADAS-Cog-12 in any analysis. A treatment effect toward benefit was observed with crenezumab on the CDR-SB at Week 73. However, in the exploratory analysis (MMSE, 22–26), the treatment effect was in the direction of greater decline. A treatment effect was also observed on the Alzheimer's Disease Cooperative Study-Activities of Daily Living Inventory (ADCS-ADL); however, it was not accompanied by a clear effect on cognition, particularly in the mildest patients. More detail on Phase II results can be found in the crenezumab Investigator's Brochure. When taken together, these data showed a consistent treatment effect only when a 2.5-fold higher exposure of crenezumab was attained (see Section 1.2.5 for further information on the pharmacokinetics of crenezumab).

Data from the Phase II program also showed that patients with milder disease (i.e., MMSE, 22–26) received greater treatment benefit. Similar findings were observed in the

biomarker Study ABE4955g. In the more recent 18-month Phase III global program with anti-amyloid antibodies in mild to moderate AD, solanezumab failed to meet primary endpoints on cognition and function. However, treatment effects were observed in a prespecified secondary analysis of pooled data from patients with mild AD data from the EXPEDITION1 and EXPEDITION 2 studies ([Doody et al. 2014](#)), which showed a statistically significant effect on cognition (ADAS-Cog subscales 11 and 14) and a trend on function (ADCS-ADL). No clinical benefit was observed in patients with moderate AD on any clinical scale, which supported the hypothesis that intervention is needed early in the course of disease.

AD is a slow, progressive disorder with no fixed events that define its onset ([Albert et al. 2011](#)). As AD is symptomatic long before dementia is diagnosed, pAD is recognized as an intermediate stage between normalcy and dementia. According to this approach, Dubois et al. ([2014](#)) proposed the diagnosis of early AD on the objective evidence of significantly impaired memory and the presence of hippocampal atrophy on MRI, an abnormal pattern of CSF biomarkers, or a specific pattern on PET neuroimaging. This approach includes pAD and mAD, irrespective of the dementia diagnosis. Because the accumulation of brain amyloid begins before the onset of AD dementia, it is reasonable to postulate that the benefit of anti-amyloid therapy may be greater if initiated at this earlier stage of the disease while neuronal damage is more limited. This supports enrollment of patients who have detectable but more subtle cognitive deficits but have confirmed pathophysiology.

The use of a single endpoint across both subpopulations of pAD and mAD is consistent with the current understanding of AD. Use of the CDR-SB as the primary outcome measure for studies of prodromal to mild AD enables simultaneous demonstration of benefit on primary symptoms (e.g., cognition, function) and clinical relevance ([Aisen 2009](#); [Aisen et al. 2011](#)) while also ensuring use of a clinical outcome assessment with adequate measurement properties ([U.S. Food and Drug Administration \[FDA\] 2013](#)).

The approach to population and appropriate primary endpoint is used by others and many clinical programs now target the prodromal to mild AD continuum and use the CDR-SB to measure treatment benefit (see AMARANTH [NCT02245737] and PRIME [NCT02477800]).

Collectively, the data support the rationale and strategy for conducting Phase III efficacy and safety studies with crenezumab in patients with prodromal to mild AD who have biomarker (CSF or PET) evidence of amyloid pathology.

The purpose of this study is to establish efficacy and safety of crenezumab in patients with prodromal to mild AD who may or may not be treated concurrently with approved treatments for AD.

As anti-amyloid therapy is not expected to provide acute improvement of symptoms, a minimum of a 100-week, 26-dose treatment period was selected to demonstrate enduring clinical benefit on the basis of the mechanism of action of crenezumab that is expected to delay disease progression rather than provide symptomatic improvement over baseline. The proposed trial duration is supported by data from Study ABE4869g, which demonstrated that the difference in decline between placebo- and crenezumab-treated patients' increased over time. Placebo decline is expected to be greater at 24 months relative to 18 months; this greater decline allows greater potential to demonstrate treatment effect.

The use of the OLE enables a longer assessment of benefit-risk in the target population among a large proportion of patients who enter the study and enables those who received placebo in the double-blind portion of the trial to obtain the potential benefit of active treatment.

### **1.3.3            Dose**

[figure not shown]
Given the very limited brain penetration observed for IgGs in general (0.2%–0.3% of levels in serum; [Reiber and Felgenhauer 1987](#)), high-serum drug concentrations will be required to increase exposure to the site of action.

The Phase II studies demonstrated consistent treatment effects in the high-dose (15 mg/kg q4w IV) arm without eliciting dose-limiting events. The therapeutic window for crenezumab has not been fully explored; increasing the dose in this study has the potential to increase efficacy while maintaining a favorable safety profile.

Higher doses of crenezumab are predicted to increase concentrations in the brain compared with the 15 mg/kg IV dose and therefore maintain drug concentrations above the in vitro EC50 in the brain throughout the treatment period. In vitro, the EC50 for crenezumab binding to A $\beta$ 1-42 monomers and aggregates was approximately 0.2  $\mu$ g/mL and higher target engagement of soluble A $\beta$  was observed with higher crenezumab concentrations ([Adolfsson et al. 2012](#)). Crenezumab binds both A $\beta$ 1-40 and A $\beta$ 1-42 with high affinity (7.3  $\pm$  0.6 nM and 11.1  $\pm$  1.2 nM, respectively), inhibits A $\beta$  aggregation, and promotes A $\beta$  disaggregation. The dose of 60 mg/kg results in a 4-fold increase in exposure in all PK parameters compared with 15 mg/kg (see [Figure 1](#)).

**Figure 1 Pharmacokinetic Profile Based on Modelling and Simulation Data for 60 mg/kg of Crenezumab Administered Intravenously Every 4 Weeks Compared with 15 mg/kg Crenezumab Administered Intravenously Every 4 Weeks**

Conc=concentration; Q4w=every 4 weeks; Dotted red line=EC50.

Nonclinical safety data provide 2-, 6-, and 3-fold safety factors for the 60-mg/kg dose at steady state on the basis of human equivalent dose, average exposure (AUC), and Cmax, respectively, relative to the maximum tested dose of 100 mg/kg per week via SC administration in cynomolgus monkeys (see the crenezumab Investigator's Brochure).

The dose used in this study, 60 mg/kg IV q4w, along with higher doses, is being evaluated in the ongoing Phase Ib Study GN29632 (see Section 1.2.2.6). This study was designed to provide evidence of absence of early safety signals for higher doses of crenezumab than had been used in the completed Phase II program. All patients in this study are able to continue into an OLE. Up to the date of this protocol, no stopping criteria had been met (including no occurrences of ARIA-E), and no serious adverse events related to study drug had been observed. Patients who reached 13 weeks of treatment all transitioned to an OLE.

In this Phase III study, use of a higher dose (60 mg/kg) q4w than previously used in the Phase II program has been selected as it provides the opportunity to determine the optimal benefit-risk for patients.

### **1.3.4 Biomarkers**

In AD, core biomarkers that have been developed that reflect amyloid and neurofibrillary tangle pathology, and neuronal degeneration. Additional biomarkers that reflect other aspects of Alzheimer's pathology are also being developed.

Two imaging modalities are mainly used as secondary or exploratory endpoints in clinical trials of AD: structural MRI and amyloid PET. The change in volumes of specific brain regions as measured by structural MRI is thought to reflect neuronal loss and atrophy. PET tracers that bind to fibrillar A $\beta$  in the brain (e.g., florbetapir, approved for use by the FDA in 2011) are thought to represent accumulation of the A $\beta$  plaques (Joshi et al. 2012).

The CSF is in direct contact with the extracellular space of the brain and biomarkers measured in CSF can reflect biochemical changes in the brain. Low CSF A $\beta_{42}$  is well established as a biomarker of Alzheimer's pathology (Shaw et al. 2009; Le Bastard et al. 2013). Thus, CSF A $\beta$  levels may provide information on diagnosis and disease progression and act as a biomarker for target engagement and for the impact of crenezumab on A $\beta$  retention and aggregation. Changes in CSF total tau and p-tau-181 levels over time may provide information on the impact of crenezumab on tau pathology. Other exploratory biomarkers in CSF may provide additional understanding of the impact of crenezumab on disease progression.

### **1.3.5 Risk to Patients without Alzheimer's Disease Pathology**

Due to rigorous screening procedures in this study, including the measurement of CSF A $\beta_{1-42}$  and amyloid-PET scan, it is expected that only patients with AD pathology will be enrolled. In the event that a patient without amyloid pathology is enrolled, no additional risk is expected. However, such a patient may experience other side effects related to the product (e.g., infusion reactions, development of ADAs).

### 1.3.6 Overall Benefit-Risk Summary

The benefit-risk profile of investigation of crenezumab at a dose of 60 mg/kg IV q4w in a population of prodromal to mild AD patients is favorable.

Overall, the benefit-risk assessment of crenezumab is based on the following:

- In Phase II studies *in patients with AD*:
  - In prespecified subanalyses, a consistent effect on ADAS-Cog-12 was observed in the subset of patients with mAD (MMSE, 22–26) who were treated with crenezumab 15 mg IV q4w versus placebo.
  - Treatment with crenezumab was associated with an increase in CSF-A $\beta$ 42 relative to placebo, which was suggestive of target engagement in the CNS.
  - ARIA events were within the range of background events in this population. *A single patient experienced three events of asymptomatic ARIA-E, all of which were Grade 1 in severity.*
  - ARIA *appears* to be manageable with MRI monitoring and dose-intervention algorithms and do not appear to lead to significant adverse outcomes (e.g., [Sperling et al. 2012a](#))
    - While more deaths and pneumonia cases were observed with crenezumab versus placebo, there was no pattern seen in the causes of death, and no obvious common mechanism observed for pneumonia (e.g., immunosuppression). In addition, death rates are in line with background rates for the placebo-treated or untreated AD population ([Henley et al. 2014](#)) and in the variability range reported in clinical trials for compounds of this class with similar patient populations and durations of treatment ([Doody et al. 2014](#); [Salloway et al. 2014](#)). The rate of pneumonia in crenezumab-treated patients (3.2%) is within the reported incidence of pneumonia in the elderly population (2.5%–4.4%; [Chong and Street 2008](#)), and slightly higher than the rate of pneumonia cases reported in the active and placebo arms of the solanezumab Phase III trials (2.0% and 2.1%, respectively; [Doody et al. 2014](#)). This may be attributable to the small patient numbers in the Phase II studies.
- *Until January 2018, in the ongoing clinical development program two additional ARIA-E (one symptomatic) have been observed. The benefit–risk profile remains unchanged by these adverse events.*
- Patients will undergo regular brain MRI monitoring, and discontinuation rules are in place in case of ARIA.
- Patients will be asked about prior respiratory history and any risk factors for pneumonia at screening. Those with significant respiratory disease (such as severe chronic obstructive pulmonary disease [COPD]) will be excluded. Pneumonia cases, other serious respiratory infections, and deaths will be closely monitored in the study, through the requirement to report these cases to the Sponsor within 24 hours with a full description of the case (see Section 5.4).

- An unblinded iDMC is in place to review adverse events, serious adverse events, ARIA-E and ARIA-H findings, and adverse events of special interest (including pneumonia) as well as laboratory and ECG data. Review will occur regularly (e.g., quarterly). Details of the iDMC will be provided in the iDMC Charter (available on request).

## **2. OBJECTIVES AND ENDPOINTS**

This study will evaluate the efficacy, safety, and pharmacokinetics of crenezumab compared with placebo in patients with prodromal to mild AD. Specific objectives and corresponding endpoints for the study are outlined in [Table 1](#).

**Table 1 Objectives and Corresponding Endpoints**

Objectives	Corresponding Endpoints
Primary Efficacy Objective:	

 
To evaluate the efficacy of crenezumab compared with placebo
 
	
 
Change from baseline to Week 105 in global outcome as assessed by CDR-SB
 

Secondary Efficacy Objectives:	

 
To evaluate the efficacy of crenezumab compared with placebo on additional cognitive, functional, and behavioral outcomes
 
	
 
Change from baseline to Week 105 on cognition as assessed by ADAS-Cog-13 and ADAS-Cog-11
 
Change from baseline to Week 105 on severity of dementia, assessed by CDR-GS and MMSE
 
Change from baseline to Week 105 on function as assessed by the ADCS-ADL total score and its ADCS-iADL subscore and by the FAQ total score
 
Change from baseline to Week 105 on a measure of dependence derived from the ADCS-ADL score
 
Change from baseline to Week 105 on behavior assessed by the NPI-Q total score
 

 
To evaluate the efficacy of crenezumab compared with placebo on caregiver and quality of life endpoints
 
	
 
Effect of crenezumab on HRQOL, assessed using the QOL-AD scale
 
Effect of crenezumab on caregiver burden, assessed using the ZCI-AD scale
 
Effect of crenezumab on health outcomes in patient and caregiver as measured by EQ-5D
 

Exploratory Efficacy Objectives:	

 
To evaluate the efficacy of crenezumab compared with placebo on events related to disease progression
 
	
 
Effect on cognition, assessed by time to an increase from baseline at any time before or on Week 105 (i.e., worsening) on a version of the ADAS-Cog or the MMSE
 
Time to clinically evident decline since baseline, as defined by an increment on the CDR global score
 
Time to development of impairment in additional domains or worsening of impairment within a domain on the CDR-SB
 
Time to increase-of-dependence level, as derived from the ADCS-ADL scale
 
Time to decline in ability to perform one or more basic or instrumental ADL present at baseline using the ADCS-ADL scale
 
Composite time-to-event endpoint. Combination of clinical progression events including any of the following: worsening disease severity (e.g., CDR Global), increasing care needs (e.g., ADCS-ADL derived dependence level), concomitant medications, and other events that may be indicative of disease progression.
 

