## **PROTOCOL AMENDMENT, VERSION BN29553: RATIONALE**

Protocol BN29553 has been amended to clarify the study's secondary and exploratory objectives and planned statistical analysis. Additional minor changes have been made to improve protocol clarity.

The main changes to the protocol, along with a rationale for each change, are summarized below:

- Secondary efficacy objectives in Table 1 have been restructured into the following categories: a) cognitive, functional, and behavioral outcomes and, b) caregiver and quality-of-life endpoints (Section 3.3.9). Exploratory efficacy objectives have also been added, and endpoints have been amended, specifically:
  - The secondary endpoint, Alzheimer's Disease Assessment Scale-Cognitive (ADAS-Cog 12) has been changed to ADAS-Cog 11 as it affords a more differentiated endpoint from the ADAS-Cog13 endpoint. A Mini Mental State Examination (MMSE) change from baseline to Week 105 has been added to assess severity of dementia because this scale is a widely used instrument to approximate stage of disease.
  - The time-to-clinically-evident-decline endpoint has been removed since the complex scale-based composite endpoint originally proposed is no longer considered to have clinical validity. Instead, a number of exploratory efficacy endpoints aiming to enable "time to clinically meaningful event"-type analyses have been added as they may be clinically useful yet rarer and not well studied event endpoints with which to assess and describe the drug's potential efficacy. These event endpoints will be more clearly defined in the Statistical Analysis Plan.
- The pharmacokinetic and biomarker objectives and endpoints in Table 1 have been restructured and updated for clarity.
- The protocol statistical considerations and analysis plan have been revised as follows:
  - Sample size re-estimation text has been added to Section 6.1 (Determination of Sample Size) as is commonly done in pivotal studies. In the event the variability of the Clinical Dementia Rating-Sum of Boxes (CDR-SB) endpoint is observed to be greater than planned, the proposed sample size increase will reduce the risk of an underpowered study, thereby reducing the risk of having less than 80% power to reach significance when the true relative reduction in CDR-SB equals 30%.
  - Wording has been updated at the end of Section 6 to clarify the population that will not be part of the primary analyses.

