
 
To evaluate the efficacy of crenezumab compared with placebo on events related to disease progression
 
	
 
Effect on cognition, assessed by time to an increase from baseline at any time before or on Week 105 (i.e., worsening) on a version of the ADAS-Cog or the MMSE
 
Time to clinically evident decline since baseline, as defined by an increment on the CDR global score
 
Time to development of impairment in additional domains or worsening of impairments within a domain on the CDR-SB
 
Time to increase-of-dependence level, as derived from the ADCS-ADL scale
 
Time to decline in ability to perform one or more basic or instrumental ADL present at baseline using the ADCS-ADL scale
 
Composite time-to-event endpoint. Combination of clinical progression events including any of the following: worsening disease severity (e.g., CDR Global), increasing care needs (e.g., ADCS-ADL-derived dependence level), concomitant medications, and other events that may be indicative of disease progression
 

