## 1. **BACKGROUND**

### 1.1 **BACKGROUND ON ALZHEIMER'S DISEASE**

Alzheimer's disease (AD) is the most common form of dementia; it affects an estimated 5.3 million individuals in the United States and 46.8 million people worldwide (Alzheimer's Association 2015; Alzheimer's Disease International 2015). The disease is characterized pathologically by the accumulation of extracellular  $\beta$ -amyloid ( $A\beta$ ) plaques and intracellular neurofibrillary tangles in the brain. Diagnosis is made through the clinical assessment of the neurologic and neuropsychiatric signs and symptoms of AD and the exclusion of other causes of dementia. Approved medical therapies that inhibit acetylcholinesterase (AChE) activity or antagonize N-methyl-d-aspartate (NMDA) receptors in the brain may temporarily improve the symptoms of AD in some patients but do not modify progression of the disease (Cummings 2004). See the crenezumab Investigator's Brochure for further details on the pathology of AD.

AD has *until recently* been diagnosed at the clinical dementia stage. There is great variation in the course of the disease. However, *it has commonly been classified into stages by a brief cognitive screening examination, the Mini Mental State Examination (MMSE; Folstein et al. 1975)* which ranges from a score of 30 (cognitively normal) to 0 (fully impaired). MMSE scores of around 20–26 are typically associated with mild AD, 10–19 with moderate AD, and < 10 with severe AD (Dash and Villemarete-Pittman 2005). *Although the progressive deterioration in AD is categorized into these three stages: mild, moderate, and severe, it more realistically resembles a continuum (Alzheimer's Association 2015).*

AD is a slowly progressive disorder with no fixed events that define its onset (Albert et al. 2011). Prior to a diagnosis of dementia, an individual may experience problems with memory, thinking, judgment, and language, but not to a degree sufficient to impact day-to-day life or normal functional activities. This pre-dementia stage is commonly referred to as mild cognitive impairment (MCI); MCI alone is not sufficient to predict AD. *According to research criteria that have recently become available (Albert et al. 2011), the diagnosis of AD can be made with more certainty at the MCI stage with the help of biomarkers, and may then be called "MCI due to AD" or "prodromal AD (pAD)".*

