  - Examples of contraceptive methods with a failure rate of < 1% per year include bilateral tubal ligation, male sterilization, established proper use of hormonal contraceptives that inhibit ovulation, hormone-releasing intrauterine devices, and copper intrauterine devices.
  - The reliability of sexual abstinence should be evaluated in relation to the duration of the clinical trial and the preferred and usual lifestyle of the patient. Periodic abstinence (e.g., calendar, ovulation, symptothermal, or postovulation methods) and withdrawal are not acceptable methods of contraception.
- For men: agreement to remain abstinent (refrain from heterosexual intercourse) or use contraceptive measures, and agreement to refrain from donating sperm, as defined below:
  - With female partners of childbearing potential or pregnant female partners, men must remain abstinent or use a condom during the treatment period and for at least 8 weeks after the last dose of study drug to avoid exposing the embryo. Men must refrain from donating sperm during this same period.
  - The reliability of sexual abstinence should be evaluated in relation to the duration of the clinical trial and the preferred and usual lifestyle of the patient. Periodic abstinence (e.g., calendar, ovulation, symptothermal, or postovulation methods) and withdrawal are not acceptable methods of contraception.
- Evidence of the AD pathological process, by a positive amyloid assessment either on CSF  $A\beta_{1-42}$  levels as measured on the Elecsys  $\beta$ -Amyloid(1-42) Test System OR amyloid PET scan by qualitative read by the core/central PET laboratory.
- Demonstrated abnormal memory function at *FCSRT/MMSE consent* or at *main screening* [FCSRT cueing index  $\leq 0.67$  AND free recall  $\leq 27$ ]
- Evidence of retrospective decline confirmed by a diagnosis verification form (see [Appendix 4](#))

- Mild symptomatology, as defined by a screening MMSE score of  $\geq 22$  points and CDR-GS of 0.5 or 1.0. MMSE may be performed at *FCSRT/MMSE consent* or *main* screening.
- Meets NIAAA core clinical criteria for probable AD dementia (see [Appendix 2](#); [McKhann et al. 2011](#)) or pAD (consistent with the NIAAA diagnostic criteria and guidelines for MCI; [Appendix 3](#); [Albert et al. 2011](#))

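### The exploratory cognition event calls an increase on the ADAS-Cog or the MMSE worsening; for the MMSE that direction is wrong and the definition contradicts itself

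*Combined protocol and SAP*

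**What the plan says.** Section 2, Table 1, lists time-to-event endpoints under the exploratory objective "To evaluate the efficacy of crenezumab compared with placebo on events related to disease progression". The first is an effect on cognition, measured as the time to "an increase from baseline at any time before or on Week 105 (i.e., worsening) on a version of the ADAS-Cog or the MMSE". The synopsis table has the same rule: "assessed by time to an increase from baseline at any time before or on Week 105".

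Section 1.1 gives the direction of the MMSE, "which ranges from a score of 30 (cognitively normal) to 0 (fully impaired", and stages the disease accordingly: "MMSE scores of around 20–26 are typically associated with mild AD, 10–19 with moderate AD, and < 10 with severe AD".

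Section 6.4.3 analyses the time-to-event endpoints by Kaplan-Meier, a stratified Cox model (hazard ratio with 95% CI) and a stratified log-rank test at the two-sided 5% level. It gives no direction and no point threshold for this event. The amendment rationale says of the new event endpoints: "These event endpoints will be more clearly defined in the Statistical Analysis Plan". The text supplied contains no such definition for this one.

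**The concern.** The rule sets one direction, upward, for two scales. Nothing in the documents conflicts with that for the ADAS-Cog. On the MMSE a rise is improvement, so *increase* and its gloss of worsening cannot both hold.

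The wording is current text in two places, not amendment history. Other rows of the same list match direction to measure: a rise in the CDR global score, a rise in dependence, a loss of ability in daily activities. Only the MMSE gets the wrong sign.

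If the MMSE part were programmed from the word *increase*, patients who improved or fluctuated upward would be counted as progression events, and patients who declined would not. A hazard ratio for progression would then be reported on events that are not progression.

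**Working it through.** **Direction.** On the protocol's own description, MMSE worsening is a change from baseline below 0. The written event is a change above 0. At any one visit no patient can satisfy both.

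**Can the literal event occur?** Yes. Section 4.1 requires a screening MMSE of at least 22, which leaves room to rise by up to 30 − 22 = 8 points. Appendix 1 schedules the MMSE after baseline at Weeks 25, 53, 77 and 105, so there are four occasions for an upward fluctuation.

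**Plan figure to reproduce.** None. The documents give no event rate, threshold, hazard ratio or power for this endpoint, and no MMSE planning values.

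**Illustration (all inputs assumed).** The 30% slowing is borrowed from the CDR-SB assumption in Section 6.1. The other inputs are not from the documents.

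- Decline over two years: Sᵢ ~ N(m, 3.5²) on placebo and N(0.7m, 3.5²) on drug, with m = 3, 4 or 5 points.
- MMSE change at visit j: Dᵢⱼ = round(−Sᵢtⱼ + eᵢⱼ − eᵢ₀), with tⱼ = 24/104, 52/104, 76/104, 104/104 and e of SD 1.5.
- MMSE event with threshold k = 1 or 3 at any visit: correct sign Dᵢⱼ ≤ −k; literal reading Dᵢⱼ ≥ k.
- ADAS-Cog worsening: 2Sᵢtⱼ plus the difference of two errors of SD 3, at or above 2k.
- 100,000 patients per arm, unstratified Cox fit, no dropout, no ceiling at 30.

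Hazard ratios, drug against placebo:

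| m | k | MMSE decrease | MMSE increase (literal) | ADAS-Cog or MMSE decrease | ADAS-Cog or MMSE increase (literal) |
|---|---|---|---|---|---|
| 3 | 1 | 0.90 | 1.17 | 0.93 | 0.98 |
| 3 | 3 | 0.84 | 1.30 | 0.85 | 0.93 |
| 4 | 1 | 0.89 | 1.24 | 0.92 | 0.96 |
| 4 | 3 | 0.81 | 1.44 | 0.83 | 0.89 |
| 5 | 1 | 0.87 | 1.33 | 0.91 | 0.95 |
| 5 | 3 | 0.78 | 1.65 | 0.80 | 0.85 |

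For example, with m = 4 and k = 3 the literal MMSE event occurs in 13.7% of placebo and 19.5% of drug patients. The correctly signed event occurs in 73.5% and 63.9%.

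With only four event times, the tie handling in this fit pulls the ratios towards 1. As a check, ln(1 − p_drug)/ln(1 − p_placebo) for the two extreme literal MMSE cases gives ln(0.482)/ln(0.545) = 1.20 and ln(0.841)/ln(0.901) = 1.66. The direction and approximate range are unchanged.

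**Reading.** The MMSE-only event flips direction, though not to the exact reciprocal. The combined event stays below 1 but moves towards it (0.85 to 0.98, against 0.80 to 0.93). An ADAS-Cog-only event does not use the MMSE rule.

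**The case against.** The best defence is that the intent is plain. The sentence itself says worsening, and the row's objective is disease progression. The bullet also cannot be programmed as it stands: it gives no threshold, leaves the ADAS-Cog version open and does not say which instrument counts. The amendment rationale leaves those details to the SAP. MMSE change to Week 105 is separately a secondary endpoint analysed by MMRM, where the sign is not in doubt, so a reversed event analysis would be noticed.

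Most of this stands. A reader might infer that the endpoint as written counts improvers as progressors and reverses the hazard ratio. The documents do not support that. They give two incompatible directions for the MMSE, one of them right, and no coded rule. Reversal needs an MMSE-only event and a programmer who follows *increase* and ignores both the gloss and the objective.

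A reader might also put a single figure on the reversal from Week 105 alone. With assumed mean changes of −4.0 and −2.8 and SD 4, P(change > 0) is 1 − Φ(1.0) = 0.159 on placebo and 1 − Φ(0.7) = 0.242 on drug, and ln(0.758)/ln(0.841) = 1.60. That is not this endpoint, which counts an increase at any visit. Any-visit checks with similar assumed inputs gave about 1.3 to 1.4.

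The defence does not remove the contradiction. Leaving detail to the SAP does not correct a wrong sign in the protocol: a correct SAP definition would have to depart from the protocol's word.

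**Conclusion.** Wrong as written, and minor. That the sign is wrong for the MMSE follows from the protocol's own text and needs no assumption.

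The consequence is conditional. Under literal coding, a 30% slowing of decline would show a hazard ratio of about 1.2 to 1.65 for an MMSE-only event. A combined event would be diluted and an ADAS-Cog-only event unaffected. These ranges rest entirely on assumed decline, variability and thresholds; they show direction and are not a forecast.

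The endpoint is exploratory and outside the fixed testing sequence in Section 6.4.2. The primary and key secondary results, alpha and sample size are unaffected.

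**What to change.** In the synopsis and Table 1, give each scale its own direction, for example: *time to first worsening from baseline, up to and including Week 105, where worsening is an increase on the ADAS-Cog or a decrease on the MMSE*. Carry the same directions into the SAP definition of the event, which should also give the point threshold, the ADAS-Cog version and whether one instrument or either one counts.

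The cost is one phrase in two protocol tables and one SAP definition, with no change to data collection, sample size or the testing hierarchy. It should be done before unblinding, because a direction settled afterwards could look data-driven.
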